Orlistat is an over-the-counter weight-loss aid that preferentially reduces body fat compared to diet and exercise alone. Our primary outcome is weight loss. Our secondary outcome is the change in concentration of chemicals that are stored in body fat (POPs). We hypothesize that the Orlistat group will lose more weight than the placebo group and because Orlistat preferentially reduces fat, that the weight loss in the Orlistat group will be accompanied by a reduction in serum levels of fat-soluble chemicals (POPs). Eligible individuals (using stricter criteria than recommended by FDA), will be randomized to Orlistat or placebo taken 3x daily with food. Both groups will receive multivitamins and a program of diet and exercise for six months.

Objectives:

To explore whether weight loss associated with Orlistat has a secondary effect of reducing blood levels of PBB and other POPs

Endpoints:

Primary Endpoint: Weight loss

Secondary Endpoint: Change in serum concentrations of PBBs, PCBs, DDE, and PBDE.

Study Population:

We will conduct this study among individuals exposed to polybrominated biphenyls (PBB) as the result of an industrial accident. We estimate we will need to enroll approximately 120 individuals into the trial to have 100 complete the 6-month trial duration. Healthy men and women, aged ≥ 18 with a BMI ≥ 25 and at high risk for a PBB level ≥ 1 part-per-billion or a recently measured PBB level ≥ 1 part-per-billion will be screened for additional health-related eligibility criteria. We will NOT enroll individuals with contra-indications for Orlistat and will have more stringent inclusion criteria than recommended by the FDA for Orlistat.

Description of Sites/Facilities

Participants will be enrolled by telephone from Emory University or enrolled in-person by Emory staff in Michigan.

Enrolling Participants:**Description of Study Intervention:**

Random assignment to Orlistat at the over-the-counter dose (60 mg capsule, up to three times daily with fat-containing meals) or placebo capsule. Diet and exercise plus a daily multivitamin will also be recommended and monitored for both groups.

Study Duration:

Approximately three years.

Participant Duration:

Six months

Figure 2: Schedule of Activities

Procedures	STUDY CALENDAR				
	Screening		Time (months) ± 2 weeks		
	1	2	Enroll ment	3	6
Review previously collected data for provisional eligibility	X				
Informed Consent		X			
Telephone screen for additional eligibility criteria		X			

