Online comprehensive health questionnaire (CHQ) or update of previous health questionnaire		X			
Blood draw for clinical function blood tests (liver, kidney, thyroid); review for eligibility and return results to individuals		X			X
Anthropometry (weight, height, waist circumference)		X		X	X
Blood draw for serum POPs concentrations		X		X	X
Analyses of serum POPs concentrations (baseline, 3 mo., 6 mo.)	After all samples collected				
Randomization			X		
Dietary Assessments			X	X	X
Physical activity assessments			X	X	X
Pill count to check adherence			Months 3, 6		
Compensation			\$40	\$60	
Initiate a weekly telephone call – to answer questions, encourage adherence and determine any adverse events or new health problems – then reduce frequency of calls depending on each patient's needs and preference.			Months 1 -6		
Medication dispensed (Orlistat or placebo)			Enrollment: 3 mo. supply Month 3: 3 mo. supply		
Multivitamins dispensed (200ct)			X		
Post-study follow-up telephone calls			One week and one month after completion		

Study Design Overview: A randomized, double-blind, placebo-controlled 6-month trial will be conducted among selected participants from the PBB Registry. Signed informed consent will be obtained, in person or online, after discussion with study staff and an opportunity to ask questions. Potential participants will be screened for eligibility by self-report of health information and clinical laboratory tests. Study participants will be randomized into one of two groups: the Orlistat (intervention) group or the control (placebo) group. Both groups will be prescribed the same diet and exercise regimen.

Anthropometry measurements (weight, height, waist circumference) will be obtained at enrollment and serum levels of PBB, PCB, DDT/DDE and PBDE (POPs) will be measured at enrollment, at 3 months and at 6 months (all chemical analyses will be done at the conclusion of the trial). We will determine if body weight and serum concentrations of POPs have changed over time in each group. Subgroup analyses by amount of weight loss, enrollment PBB concentration, and gender will be undertaken as well. Data will be analyzed to see if the Orlistat group experiences greater weight loss than placebo and secondarily, whether the Orlistat group experiences a greater reduction in serum POPs over the course of the trial.

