The statistical hypothesis of interest is whether a mean change in weight or serum levels of POPs is detected at six months from the baseline. $H_0: \delta_I - \delta_P = 0$ vs $H_a: \delta_I - \delta_P > 0$, testing whether the mean change in weight or serum levels of POPs differs (mean change: δ , between the groups; δ_I , intervention group; δ_P , placebo group). The null hypothesis denotes no mean difference between the groups, and the one-sided alternative hypothesis denotes a difference between the groups, with the intervention group having a greater reduction in weight or serum levels of POPs over the course of the trial.

We plan to recruit and screen PBB registry participants, to enroll 120 participants into the trial. Our goal is to have 100 participants complete the 6-month trial duration. These estimates are based on the power analyses described here:

Power Analysis: The primary objective is to determine if the use of Orlistat results in weight loss in this population. Previous studies have shown an average of 2 to 3 kg weight difference between the intervention and placebo groups [16]. Assuming a standard deviation for weight change of 5 kg, we would have adequate power (80%) to detect a 2-3 kg difference ($\alpha=0.05$; $\rho=0.5$) in weight with a sample size of 50 in each group. Power analyses were performed in PASS 13 software [17].

The secondary endpoint is the change in serum concentrations of PBBs, PCBs, DDE, and PBDE at six months from the baseline. For the outcome of change in serum POP levels, we based our sample size estimations on the historical PBB data for PBB registry participants with at least 2 measurements within a year and the pilot data from Jandacek et al [18]. We estimate that the variance of the differences in PBB levels is expected to be between 0.1 and 0.2 log parts per billion (ppb) (σ^2_{diff}). We have used the pooled variances for our power calculations. From our historical data, we expect a 1% reduction in PBB levels due to the natural course of exposure. A sample size of 50 in each group, would provide at least 80% power to detect a mean change in log PBB levels of -0.1 and -0.2 log ppb with a significance level of $\alpha=0.05$.

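### The planned subgroup analysis by amount of weight loss conditions on the post-randomisation primary outcome, so any Orlistat-versus-placebo comparison inside those subgroups is not randomised

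*Combined protocol and SAP*

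**What the plan says.** The Study Design Overview lists three subgroup factors in one sentence: "Subgroup analyses by amount of weight loss, enrollment PBB concentration, and gender will be undertaken as well". It gives no cut-point, number of groups or outcome for the weight-loss subgroups. It does not say whether the arms will be compared inside them, and it does not label the analysis exploratory or non-randomised.

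The Study Description says "Our primary outcome is weight loss", and the Endpoints entry repeats it: "Primary Endpoint: Weight loss". The Study Description also hypothesises that the Orlistat group will lose more weight than placebo. The secondary endpoint is given as "Secondary Endpoint: Change in serum concentrations of PBBs, PCBs, DDE, and PBDE".

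Statistical Modeling returns to subgroups and applies them to both weight change and PBB elimination rates. Its examples are all baseline variables: age, gender, initial PBB level and initial BMI. Amount of weight loss is not among them, but the list is introduced as examples and so does not rule it out.

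**The concern.** A subgroup analysis compares randomised arms fairly only when the subgroup is fixed before treatment can influence it. Gender and enrollment PBB meet that condition. Weight loss does not: if Orlistat works as hypothesised, it moves people from the low-loss group to the high-loss group, so each group holds different kinds of people in the two arms. At a given loss, placebo participants will on average have got there with more diet, activity or other personal factors, and Orlistat participants with less.

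The consequence depends on the outcome compared. For weight, the split removes much of the effect being estimated. For serum POPs, it conditions on a possible mediator that may share causes with the outcome. The Background notes that Registry members have repeatedly asked whether losing weight lowers their PBB burden, so a table by amount of weight loss would attract attention and could be read as a treatment effect.

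**Working it through.** **Inputs from the plan (Power Analysis).** Effect: "Previous studies have shown an average of 2 to 3 kg weight difference between the intervention and placebo groups". Spread: "Assuming a standard deviation for weight change of 5 kg". Size: 50 completers per arm, alpha 0.05, one-sided alternative. Variance of the log PBB differences: 0.1 to 0.2, so SD = √0.1 to √0.2 = 0.316 to 0.447. The 2.5 kg used below is the midpoint of 2 to 3 kg and is not itself stated.

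**The plan's own figure.** It claims "we would have adequate power (80%) to detect a 2-3 kg difference". The standard error of the arm difference is 5 × √(2/50) = 1.0 kg. One-sided power is Φ(difference/1.0 − 1.645): 0.64 at 2 kg, 0.80 at 2.5 kg and 0.91 at 3 kg. The 80% is reproduced at the midpoint without using the stated correlation of 0.5. The shortfall at 2 kg is a separate matter.

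**Weight inside a median split (the split is assumed).** Let weight loss be normal with SD 5 in both arms, with mean 0 on placebo (an arbitrary origin) and 2.5 on Orlistat. By symmetry the pooled median is 1.25 kg, which is 0.25 SD above the placebo mean and 0.25 SD below the Orlistat mean. With φ(0.25) = 0.3867, Φ(0.25) = 0.5987 and Φ(−0.25) = 0.4013, the means in the lower half are:

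- Placebo: 0 − 5 × 0.3867/0.5987 = −3.23 kg
- Orlistat: 2.5 − 5 × 0.3867/0.4013 = −2.32 kg
- Difference: 0.91 kg, and the same in the upper half

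A simulation gave 0.91 to 0.92 kg. The lower half holds about 30 of 50 placebo and 20 of 50 Orlistat participants; the upper half is the reverse. True effects of 2 and 3 kg give 0.73 and 1.10 kg. The 0.91 hardly moves for an SD between 4.3 and 7 kg, but it depends strongly on the split:

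| Split, true effect 2.5 kg | Arm difference inside groups (kg) |
|---|---|
| Halves | 0.91 / 0.91 |
| Tertiles | 0.70 / 0.16 / 0.70 |
| Quartiles | 0.60 / 0.10 / 0.10 / 0.60 |
| One fixed cut, from 5 kg below to 7.5 kg above the placebo mean | 0.43 to 1.76 |

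Every split examined shrinks the effect.

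**Serum PBB inside a median split (the correlation is assumed).** Suppose Orlistat has no effect on PBB, but within each arm weight change and log PBB change are correlated at r through shared causes. Inside each half the arms then differ in those causes by (true effect − within-half difference)/5 SD units, and the spurious PBB difference, against Orlistat, is r × SD of log PBB change × that gap.

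- Low end: effect 2 kg, r = 0.2, SD 0.316. Gap (2 − 0.728)/5 = 0.254; bias 0.2 × 0.316 × 0.254 = 0.016 log ppb.
- High end: effect 3 kg, r = 0.5, SD 0.447. Gap (3 − 1.095)/5 = 0.381; bias 0.5 × 0.447 × 0.381 = 0.085 log ppb.

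The smaller change the plan is powered for is −0.1 log ppb. A simulation at 2.5 kg, with a shared cause correlated 0.5 with weight loss, gave about +0.03 in each half. With no shared cause it gave zero. If r is negative, the bias favours Orlistat.

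**The case against.** The strongest reply is that the plan does not describe the damaging analysis. The sentence names no outcome. The sentence before it concerns change within each group, and the comparison between arms comes only afterwards. Given the stated objective, a natural reading is POP change by amount of weight loss. Comparing weight between arms inside weight-loss groups would be close to circular. Statistical Modeling does not carry the factor forward. On that view this is loose wording in an overview paragraph.

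Much of this stands. The outcome is undefined, and serum POPs are at least as natural a reading as weight. If only POPs are meant, the 0.9 kg figure is irrelevant. It is also fair that the PBB bias is below one standard error: with 30 against 20 participants in a half, the standard error is SD × √(1/30 + 1/20) = 0.289 × SD, or 0.09 to 0.13 log ppb.

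It does not dispose of the point. The analysis is stated as one that will be done, and weight loss is listed on the same footing as gender, for which comparing arms within subgroup is legitimate. Statistical Modeling says subgroups serve to assess differences in weight change or PBB elimination. It also links physical activity both to lower weight and, possibly, to lower PBB burden, so a shared cause is plausible on the plan's own account. Nothing elsewhere labels or limits the analysis.

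Three stronger readings are tempting and are not supported. A reader might infer that the plan fixes the shrinkage at about 0.9 kg; only the direction is fixed, because no split is stated. A reader might infer that the primary result is compromised; the intention-to-treat mixed model with its group-by-time term does not use these subgroups. A reader might infer that the analysis would make Orlistat appear to raise PBB; that needs a positive correlation from shared causes, which the documents do not quantify.

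**Conclusion.** The concern holds in a limited form. Amount of weight loss is a post-randomisation variable and the primary outcome, and the plan treats it as if it were a baseline subgroup factor. Any arm comparison inside those subgroups is non-randomised.

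For weight, attenuation is certain in direction but not in size. The median-split illustration rests on normal changes with equal SD and the 2.5 kg midpoint. For POPs, size and sign are both undetermined; the range shown is an illustration resting on an assumed correlation and no true drug effect on PBB.

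The primary and secondary intention-to-treat comparisons are untouched, so this is a correction that should be made to a supporting analysis and not a threat to the trial's main conclusions.

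**What to change.** In the Study Design Overview, remove amount of weight loss from the subgroup list and limit between-arm subgroup analyses to baseline factors: enrollment PBB concentration, gender, initial BMI and age. This matches the examples in Statistical Modeling and reconciles the two sections.

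Keep the scientific question by adding a sentence that the relation between weight change and POP change will be reported as an exploratory, non-randomised association, with no arm comparison inside weight-loss groups.

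The possible adjustment of PBB models for change in BMI, in Statistical Modeling, is a separate matter; altering it would not correct this sentence.

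The cost is a small wording change and the loss of one subgroup table that has no causal reading. Sample size, data collection and the primary model do not change.

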Participants will be contacted upon expected receipt of study materials. Contact will be established weekly, then reduced as the study proceeds. The frequency of contact will depend on the individual needs/preferences of each participant until the conclusion of the trial at 6 months. Adherence will be monitored by these telephone calls and intervals of compensation. All participants will be asked to report pill counts to measure adherence at 3 and 6-month time points. Participants will also be asked at each study phone call whether they are experiencing any adverse symptoms potentially related to the medication or other aspects of the study.

Weight Management Intervention: The weight management intervention, dietary assessments, and physical activity assessments will be supervised by [name], MPH, RD, Professor of Epidemiology. Prior to relocating to Emory in 2013, [name] was Professor of Nutrition and Director of the Diet Assessment Center at The Pennsylvania State University. As a nutrition epidemiologist and a registered dietitian, she has approximately 20 years of experience exploring associations between

nutritional exposures and chronic disease outcomes and has designed and collaborated on multi-disciplinary trials of diet, exercise and other interventions to improve health.

Participants in both arms will follow the same study schedule with approximately equal contact time. Any contacts (e.g., in person, phone, e-mail) with the study staff will be logged to assess total contact time. We will provide weight loss and management guidance and support primarily via telephone interactions and online resources focusing on dietary and physical activity weight loss and management strategies.

Participant interactions will begin weekly then adjusted based on participant needs and preferences. This plan allows the participants to implement strategies to gradually alter their food intake to promote weight loss and maintenance. Weight loss and management strategies for both study arms will be consistent with the Orlistat recommendations of limiting overall fat intake to 30% of daily energy with energy intake altered to lose 1-2 lbs. /wk.

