Most of these risks are not serious with the exception of the last three, kidney, pancreas or liver injury. We have minimized the likelihood of these serious risks by screening potential participants for a history of kidney, liver or pancreatic abnormalities and blood tests for kidney, thyroid and liver function. These clinical screening tests are an ADDITIONAL LAYER OF PROTECTION against risk. They are not required nor recommended before initiating treatment with Orlistat. In addition, we will ask about symptoms of kidney, pancreatic or liver injury during each telephone contact. Participants will be instructed to consult their health care professional if they are experiencing symptoms of liver, pancreatic, or kidney injury possibly associated with the use of Orlistat. Symptoms of liver injury include loss of appetite, itchy skin, yellowing of the skin or the white part of the eyes, amber colored urine, light-colored

bowel movements (stools), or pain in the upper right portion of the stomach. , Signs and symptoms of pancreatitis include right upper abdominal pain, nausea, vomiting, and loss of appetite. Symptoms of kidney problems include swelling, especially of the legs and feet, little or no urine output, frequent or painful urination, blood in the urine, loss of appetite, nausea, vomiting, or severe pain in the back, belly, or groin. These serious risks are also very rare. In 2010 FDA reported 13 cases of liver failure (12 of them with the prescription dose of Orlistat which is twice the over-the-counter dose).

<https://www.fda.gov/Drugs/DrugSafety/PostmarketDrugSafetyInformationforPatientsandProviders/ucm213038.htm>
Because of this report, we will repeat liver and kidney function tests again at the conclusion of the study (at 6 months), to determine if any decline in liver or kidney function occurred during the trial.

Potential risks associated with blood draws include:

- Syncope or lightheadedness
- Hematoma
- Arterial puncture

Adequacy of Protection Against Risks*a. Recruitment and informed Consent*

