function, thyroid function, and creatinine levels will be measured prior to enrollment to ensure that the participant is healthy enough to partake in the study. Participants with abnormal levels or functions will not be eligible to participate in the study and will be counseled to seek care from their primary care physician. Additionally, participants with chronic kidney disease (defined by a glomerular filtration rate below 60) or kidney stones or gall bladder disorder will be excluded. Participants will be excluded if they are pregnant or lactating, have a diagnosed problem absorbing food, have a history of pancreatitis, bariatric surgery, organ transplantation, a diagnosed eating disorder, or a serious chronic disease as identified by the study doctor. Use of weight-loss medications, Coumadin, warfarin, Cyclosporine, or oral steroids will also exclude participants from the study. Allergies to any ingredients of the Orlistat OTC capsules including the active ingredient, Orlistat, and the inactive ingredients, microcrystalline cellulose, povidone, and xylitol will result in exclusion from the study. Participants will become ineligible at any point during the study if they begin a medical regimen involving any of the above medications.

Pancreatitis is a very rare side effect of Orlistat use. Due to the extreme rarity, no routine laboratory tests will be performed. Patients will be counseled about the signs and symptoms of pancreatitis and instructed to report any relevant symptoms to Emory study staff. Liver injury is a very rare possible side effect. We will minimize the risk of liver injury by screening individuals for abnormal liver function and counseling participants about the signs and symptoms of possible liver injury.

The PI ensures that all protocol deviations, AEs, and SAEs are reported to NIEHS and IRB according to applicable regulatory requirements.

COLLECTION AND REPORTING OF SAEs AND AEs

For this study, the following standard AE definitions are used:

Adverse event: Any unfavorable and unintended sign (including an abnormal laboratory finding), symptom, or disease temporally associated with the use of a medical treatment or procedure, regardless of whether it is considered related to the medical treatment or procedure.

Serious Adverse Event:

Any AE that results in any of the following outcomes:

- Death
- Life-threatening event
- Event requiring inpatient hospitalization
- Persistent or significant disability/incapacity

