- An important medical event based upon appropriate medical judgment of [name]

AEs are graded according to the following scale, based on their impact on the patient:

Mild:

An experience that is transient, and requires no special treatment or intervention. The experience does not generally interfere with usual daily activities. This includes transient laboratory test alterations.

Moderate:

An experience that is alleviated with simple therapeutic treatments. The experience impacts usual daily activities. Includes laboratory test alterations indicating injury, but without long-term risk.

Serious:

An experience that requires therapeutic intervention. The experience interrupts usual daily activities. If hospitalization (or prolongation of hospitalization) is required for treatment, it becomes a serious adverse event.

The study uses the following AE attribution scale to determine the likelihood that they are related to the study intervention:

Not related:

The AE is clearly not related to the study procedures (i.e., another cause of the event is most plausible and/or a clinically plausible temporal sequence is inconsistent with the onset of the event).

Possibly related:

An event that follows a reasonable temporal sequence from the initiation of study procedures, but that could readily have been produced by a number of other factors.

Related:

The AE is clearly related to the study procedures.

AEs are identified through self-report by participants via follow-up phone calls. At the beginning of the study we will have frequent telephone contact with participants (at least once/week) followed by reduced frequency as the study progresses but no less than monthly. Participants can request more frequent phone calls. Participants will be asked to contact the Emory study staff if additional adverse events occur or if they have any concerns or questions about the protocol.

All AEs are reported according to the Emory IRB AE reporting guidelines.

MANAGEMENT OF RISKS TO SUBJECTS

AEs that may be associated with the use Orlistat include:

- Headache
- Oily rectal discharge
- Urgent need to have a bowel movement
- Being unable to control bowel movements
- Oxalate kidney stones/oxalate kidney damage
- Pancreatitis
- Liver injury or failure

AE Management

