AEs are identified through self-report by participants via follow-up phone calls that occur weekly and then are adjusted based on patient's needs and preferences. Participants can request more or less frequent phone calls. Participants will be asked to contact the Emory study staff if additional adverse events occur or if they have any concerns or questions about the protocol.

Any medical condition that is present at the time that the participant is screened will be considered as baseline and not reported as an AE. However, if the study participant's condition deteriorates at any time during the study, it will be recorded as an AE.

Changes in the severity of an AE will be documented to allow an assessment of the duration of the event at each level of severity to be performed. AEs characterized as intermittent require documentation of onset and duration of each episode.

All AEs including local and systemic reactions not meeting the criteria for SAEs will be captured on the appropriate case report form (CRF). Information to be collected includes event description, time of onset, clinician's assessment of severity, relationship to study product (assessed only by those with the training and authority to make a diagnosis), and time of resolution/stabilization of the event. All AEs occurring while on study must be documented appropriately regardless of relationship. All AEs will be followed to adequate resolution

The occurrence of an adverse event (AE) or serious adverse event (SAE) may come to the attention of study personnel during interviews of a study participant presenting for medical care, or upon review by a study monitor.

If participants report gastrointestinal issues following Orlistat use, they will be counseled to reduce the fat content of their meals. If symptoms persist or more serious symptoms arise, participants will be told to discontinue the Orlistat regimen but continue with the diet and exercise plan.

The signs and symptoms of severe liver injury include loss of appetite, itchy skin, yellowing of the skin or the white part of the eyes, amber colored urine, light-colored bowel movements (stools), or pain in the upper right portion of the stomach. People who experience these signs and symptoms should contact their healthcare professional immediately.

Signs and symptoms of pancreatitis include right upper abdominal pain, nausea, vomiting, and loss of appetite.

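### The adverse-event question described for the study calls is narrower than the protocol's own adverse-event definition and should be aligned with it

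*Combined protocol and SAP*

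**What the plan says.** The question comes from Study Design & Methods, in the paragraph on participant contact just before Weight Management Intervention. At every study call participants are to be asked "whether they are experiencing any adverse symptoms potentially related to the medication or other aspects of the study".

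Four other places bear on it:

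- Figure 2 (Schedule of Activities) gives the purpose of the same calls: "to answer questions, encourage adherence and determine any adverse events or new health problems".
- Collection and Reporting of SAEs and AEs defines an adverse event as any unfavourable, unintended sign, symptom or disease with a temporal association, "regardless of whether it is considered related to the medical treatment or procedure". It also names the route of capture: "AEs are identified through self-report by participants via follow-up phone calls".
- AE Management repeats that route and sets the recording rule: "All AEs occurring while on study must be documented appropriately regardless of relationship". Among the items for the case report form it lists "relationship to study product (assessed only by those with the training and authority to make a diagnosis".
- Risks to Human Subjects adds a targeted element: "we will ask about symptoms of kidney, pancreatic or liver injury during each telephone contact".

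**The concern.** A participant can answer the question as described only by first deciding whether a symptom might be connected with the capsules or the study. The definition of an adverse event excludes that consideration, and the plan gives it to trained assessors at a later step. The question also asks about symptoms present at the time of the call, whereas the recording rule covers everything that occurs on study.

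At stake is the completeness of the safety record. An event that is not mentioned on a call may never reach the person qualified to judge it. Scheduled laboratory monitoring does little to back up the calls, since Figure 2 places the clinical blood tests only at screening and month 6. Calls start weekly but may fall to monthly, so an event can begin and end between two contacts.

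**Working it through.** No arithmetic applies: the plan states no figure on this point and the finding rests on none. The check sets the sections side by side.

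**Step 1: what the question admits.** Read literally, it imposes two conditions: the symptom is present now, and it may be related to the medication or another part of the study.

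**Step 2: what the plan requires.** The definition and the recording rule impose neither condition. AE Management also counts worsening of a condition already present at screening, and it asks for the times of onset and resolution, so resolved events are plainly in scope.

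**Step 3: where the two differ.** Crossing the two conditions gives four kinds of event.

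| Event | Required by the definition and recording rule | Requested by the question as worded |
|---|---|---|
| Present at the call, thought possibly related | Yes | Yes |
| Present at the call, thought unrelated | Yes | No |
| Resolved before the call, thought possibly related | Yes | No |
| Resolved before the call, thought unrelated | Yes | No |

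The plan requires all four kinds; the literal question requests one.

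**Step 4: order of events.** Formal relatedness is assigned by a qualified assessor to events already reported. A filter in the question acts before that step, and the later assessment cannot recover what was not mentioned.

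**Step 5: what else could fill the gaps.**

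- The purpose stated in Figure 2 would cover all four kinds if carried into the call. It states an aim, not a question.
- The organ-injury questions cover kidney, pancreatic and liver symptoms whatever the participant thinks of their cause. They do not reach other events.
- Protections Against Risk has participants report their health status by phone, weekly and later monthly, with no relatedness filter. It gives no question and no recall period. It also tells them to contact staff about changes in their health, which depends on the participant's initiative.
- Procedures, under SAE Reporting, has staff inform the principal investigator after each call of events since the previous contact. This supports a look-back period, but staff can pass on only what they were told.

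**Step 6: result.** These provisions widen the scope of the calls and partly offset the narrow question. None of them sets out a general question that matches the adverse-event definition. The one general symptom question whose content the protocol describes is the filtered one.

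**The case against.** The strongest reply is that the sentence is a narrative summary of one item in a call, not an instrument. The protocol presents it as an addition to other contact activities, and no call script is in the documents, so the words actually put to participants cannot be verified. Figure 2, the organ-injury questions, the health-status report and the look-back in the reporting procedure all point to a wider call. AE Management adds that events may come to light when a participant presents for medical care or on review by a monitor. All of this stands, and it limits what can be claimed.

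A reader might be tempted by three stronger readings, none of which the documents support:

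- *That calls ask about nothing but current, possibly related symptoms, so other events go unrecorded.* The provisions in the previous paragraph contradict this. The most that can be said is that this question does not request such events.
- *That participants are given the relatedness judgement.* AE Management reserves it for those qualified to diagnose. The wording may lead participants to filter their answers, which is a lesser matter.
- *That the comparison between arms is distorted.* Participants who notice oily discharge, a listed effect of Orlistat, could guess their assignment and attribute more symptoms to the capsule. That is plausible but not established. The Statistical Analysis section plans no between-arm comparison of adverse events, and any ratio would rest on invented reporting rates and on treating this question as the sole route of capture.

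The objection does not remove the conflict. A wider purpose stated elsewhere shows what the calls were meant to achieve, and the described question falls short of it.

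**Conclusion.** The point holds as an inconsistency between sections with a plausible consequence for safety capture. The question described for each call is narrower than the purpose in Figure 2, the adverse-event definition and the recording rule. Because self-report on calls is the stated route for identifying events, the wording can lead participants to omit events that they think unrelated or that have resolved.

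No numerical size can be given. The documents contain no event rates, no probability of reporting and no script, and the other provisions reduce the effect by an unknown amount. The conclusion assumes that the described question guides what staff ask; if the working script already asks openly, only the protocol text needs correcting. The change is worth making because the sentence conflicts with the plan's own rule and is cheap to put right.

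**What to change.** Reword the sentence on participant contact, and the matching prompt in the call script, so that staff ask at each call about any new or worsened symptom or health problem since the last contact, whether or not the participant thinks it related to the study. State that relatedness is assigned afterwards by the qualified assessor, as AE Management already provides. Keep the organ-injury questions as they are.

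The cost is one sentence and one prompt, slightly longer calls and more unrelated events to record. No visits or procedures are added.
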